## Quantitative Protocol Development Tool

The research protocol forms an essential part of a research project. It is a full description of the research study and will act as a 'manual' for members of the research team to ensure adherence to the methods outlined. As the study gets underway, it can then be used to monitor the study's progress and evaluate its outcomes.

The protocol should go into as much detail about the research project as possible, to enable the review bodies to fully understand your study.

The use of this collated consensus guidance and template is not mandatory. The guidance and template are published as standards to encourage and enable responsible research.

The document will:

- Support researchers developing protocols where the sponsor does not already use a template
- Support sponsors wishing to develop template protocols in line with national guidance
- Support sponsors to review their existing protocol template to ensure that it is in line with national guidance.

A protocol which contains all the elements that review bodies consider is less likely to be delayed during the review process because there will be less likelihood that the review body will require clarification from the applicant.

We would appreciate self-declaration of how you've used this template so we are able to measure its uptake.

Please indicate the compatibility of this template with any existing templates you already use by stating one of the following on the front of each submitted protocol:

- **This protocol has regard for the HRA guidance and order of content; OR**
- **This protocol has regard for the HRA guidance; OR**
- **This protocol does not have regard to the HRA guidance and order of content**

**STUDY SUMMARY**

It may be useful to include a brief synopsis of the study for quick reference. Complete information and, if required, add additional rows.

Study Title	From Womb to World: Creating Womb-Like Environments for Preterm Language Development
Internal ref. no. (or short title)	From Womb to World
Study Design	Other clinical trial to study a novel interventionLongitudinal study
Study Participants	Babies aged 0-12 months
Planned Size of Sample (if applicable)	150
Follow up duration (if applicable)	12 months
Planned Study Period	March 2026-August 2029
Research Question/Aim(s)	The main aim is to investigate whether exposure to a womb-like acoustic environment in NCU, including

**SHORT TITLE/ACRONYM**

	recordings of their parents, can improve language development in preterm infants later on.
--	--

**ROLE OF STUDY SPONSOR AND FUNDER**

The study sponsor is Oxford Brookes University, which assumes overall responsibility for the initiation, management, and governance of the Womb-to-World project. As sponsor, the University ensures that the study is conducted in compliance with all relevant regulations, ethical standards, and institutional policies, including data protection and participant safety. The sponsor does not directly influence the scientific design, data analysis, or interpretation of results, but oversees that appropriate procedures and risk management strategies are in place.

The project is funded by the Economic and Social Research Council (ESRC). The funder's role is limited to providing financial support for the study and monitoring progress in line with grant conditions. The funder does not have authority over the study design, conduct, data analysis, interpretation of findings, or dissemination of results. The research team retains full independence in all scientific and publication decisions.

**ROLES AND RESPONSIBILITIES OF STUDY MANAGEMENT COMMITTEES/GROUPS & INDIVIDUALS**

This project is supported by an advisory group that includes clinical staff from Neonatal Care Units (consultant neonatologists, nurses, occupational therapists, and psychologists), parents of preterm infants, and charity partners (SSNAP and Speech and Language UK). This group acts as the Patient & Public Involvement (PPI) advisory group, providing guidance and feedback throughout the study.

Roles and Responsibilities of the PPI Group:

- Provide input on study design, participant information materials, and recruitment strategies to ensure acceptability and feasibility.

**SHORT TITLE/ACRONYM**

- Advise on approaches to reduce potential barriers to recruitment and improve engagement with families.
- Contribute to the development of public engagement resources and dissemination materials to ensure findings are understandable and relevant to families and the broader public.
- Offer lived experience and professional expertise to inform the interpretation of study findings.

**Independence:**

The PPI advisory group operates independently from the sponsor (Oxford Brookes University) and the ESRC funder. While they provide guidance and feedback, the final decisions regarding study design, conduct, data analysis, and dissemination rest with the Chief Investigator and research team.

**KEY WORDS:**

Preterm infants, Early language development, Prosody acquisition, Neonatal Care Units, Womb-like auditory environment

**STUDY FLOW CHART**

[figure not shown]

Fig. 1. Overview of the Project .

**SHORT TITLE/ACRONYM**

[figure not shown]

Fig. 2. Summary of testing points.

**SHORT TITLE/ACRONYM**

**STUDY PROTOCOL**

From Womb to World: Creating Womb-Like Environments for Preterm Language Development

**1 BACKGROUND, RATIONALE and THEORETICAL FRAMEWORK**

Premature birth, defined as delivery before 37 weeks of gestation, is a significant global health issue affecting millions of infants each year. While advancements in neonatal care have increased the survival rates of preterm infants, premature infants continue to face unique challenges in their development. Numerous studies have shown that preterm birth increases the risk of cognitive deficits in the preschool and school years. In terms of language, preterm children show poorer auditory discrimination and memory, reading difficulties, poor vocabulary, a specific delay in verbal processing and reasoning, less complex expressive language and lower receptive understanding than their matched controls. Research by the PI has revealed that preterm birth affects, in particular, some aspects of early language development, specifically the acquisition of prosody—the rhythm and melody of speech—while having no significant impact on phonetics—speech sounds—or phonotactics—the rules governing sound combinations—. This indicates a developmental delay in prosodic acquisition for preterm infants, consistent with other studies.

Importantly, hearing becomes functional around 25 weeks of gestation, allowing foetuses to perceive speech in the womb. However, maternal tissues attenuate and filter out higher frequencies above 600–1000Hz, preserving speech melody and rhythm (prosody) while suppressing phonetic details, particularly consonants. As a result, prenatal auditory exposure primarily conveys prosodic information. Rhythmic sounds, like the mother's heartbeat, may act as a pacemaker, shaping early rhythm perception.

Evidence from animal models and simulations suggests that foetuses are exposed to a speech signal rich in prosodic features, further evidence has shown that foetuses can differentiate stimuli using prosodic cues. There is evidence that this prenatal experience shapes infants' perceptual abilities. For instance, newborns are already sensitive to the prosodic grouping and vocalic segments of their native language. Furthermore, studies using EEG responses in newborns demonstrated that prenatal exposure to specific changes in vowels and pitch led to

**SHORT TITLE/ACRONYM**

the recognition of these postnatally. Infants without such prenatal exposure only recognised vowel changes, suggesting that prenatal prosodic exposure is crucial for early language development.

The concept of 'prenatal prosodic bootstrapping' proposes that foetuses' learning about speech prosody in the womb serves as an anchor for language learning after birth. This early exposure to prosody is, thus, crucial for laying the foundation for later language development. Research has shown that prosody plays a central role in language acquisition, influencing various stages of language development. This includes the identification of a proto-lexicon, word segmentation, the storage and classification of words into categories such as lexical or functional, and even early morphosyntactic representations.

Preterm infants miss some or all essential prenatal prosodic exposure, potentially contributing to prosodic development delays. Developmental theories suggest that disruptions in typical brain development timing can have cascading effects. Early prosodic delays might, therefore, lead to later language deficits. Language delay impacts school readiness, academic performance, and long-term health and social outcomes. While some children catch up, many experience lasting effects on literacy, quality of life, mental health, and career success well into adulthood.

Furthermore, preterm babies in Neonatal Care Units (NCUs) encounter other significant challenges, particularly a persistent lack of speech and auditory stimulation, compounded by continuous exposure to loud noises. The NCU environment, dominated by the sounds of medical equipment and an absence of typical conversational interactions, deprives preterm infants of the rich auditory input crucial for their language development. Indeed, on average infants in NCUs are exposed to only 30 minutes of speech per day whereas foetuses experience nearly three hours of daily speech input.

Although, to our knowledge, no studies have directly examined the effects of auditory stimulation in NCUs on language development, evidence from other domains suggests potential benefits. For instance, preterm infants exposed to recordings of their mother's voice achieved full enteral feeding faster and exhibited significant heart rate improvements and auditory cortex plasticity compared to those receiving routine care.

**SHORT TITLE/ACRONYM**

## **2 RESEARCH QUESTION/AIM(S)**

This project seeks to address these challenges by creating a personalized, womb-like acoustic environment for preterm infants in NCUs. The **goal** is to investigate whether exposure to a womb-like acoustic environment including recordings of their parents, can improve language development in preterm infants. The project will compare the language development of preterm infants exposed to this womb-simulated environment with those in standard neonatal care and full-term infants.

### **2.1 Objectives**

- Design and implement a womb-like acoustic environment in the NCU using parental voice recordings and simulated sounds from the womb.
- Evaluate its effects on language development, including prosody, vocabulary acquisition, and cognitive development, comparing preterm infants exposed to the womb-like environment with those receiving standard care and full-term infants across their first year of life

### **2.2 Outcomes**

- **Prosody perception and acquisition** – the ability to detect and process the rhythm and melody of speech, assessed through experiments.
- **Vocabulary comprehension and production** – assessed through parental report questionnaires.
- **Cognitive development** – measured using standardised developmental assessments.

Secondary outcomes include:

- **Feasibility and acceptability of the womb-like acoustic environment** – including parental and clinical staff feedback.

These outcomes will allow us to evaluate whether exposure to a womb-like auditory environment can support early language and cognitive development in preterm infants and provide evidence to inform future neonatal care practices.

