## **Implementing Womb-like Environments in NCUs**

**SHORT TITLE/ACRONYM**

Final outputs will be implemented and tested in incubators, initially without infants (as part of WP1). Once extensively tested, the system will be introduced to incubators with infants having parental consent.

Participants. A total of 150 infants will be tested, accounting for a 20% attrition rate due to multiple experiments (10%) and longitudinal design (10%). This ensures sufficient participants per group (WS-PTg, SC-PTg, CO-FTg) for statistical analyses ( $\alpha=0.05$ , power=0.80, GPower 3.1). The estimate is based on effect sizes ( $d=0.59-0.80$ ) from prior studies on early speech perception and language outcomes in preterm infants. Participants will include:

- 1) Womb-simulated PT group (WS-PTg): Forty healthy preterm infants meeting five primary criteria:
  1. Gestational age  $\geq 26$  and  $\leq 34$  weeks.
  2. Absence of major cerebral damage (e.g., periventricular leukomalacia, intraventricular haemorrhage...).
  3. No indication of visual or hearing impairment.
  4. No family risks of developmental or language disorders.
  5. From monolingual English-speaking families.

Infants eligible to participate in the WS-PTg will be identified by the NCU team as soon as possible after their arrival to the unit and parents of these infants will be approached by one of the neonatal nurses to ask if they would want to take part in the project. Families who have given consent will be approached by the research team and given the necessary equipment to do the audio recordings. Meanwhile, a general recording of infant-directed speech recorded by the research team will be used until parental recordings are available. Infants will be exposed to the recordings until they are discharged from the NCU or they reach their due date.

- 2) Standard care PT group (SC-PTg): Forty healthy preterm infants who meet the same criteria outlined above will be recruited using the same strategy. Infants assigned to the SC-PTg will, when possible, be those who have already been discharged from the NCU.
- 3) Comparison FT group (CO-FTg): Forty healthy full-term infants born at  $\geq 37$  weeks who also meet criteria 2–5 outlined above.

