### **Measuring Language Outcomes**

WP3 includes three experiments on prosody development, one vocabulary measure, and one general cognitive development measure over five months.

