**SHORT TITLE/ACRONYM**

[figure not shown]
Lexical Tone		Lexical Stress	Prosodic Boundaries
Method	Central Fixation Procedure (CFP)	Head-turn Preference Procedure (HPP)	
Visual Stimuli			
Auditory Stimuli	
Two Cantonese lexical tone contrasts: Tone 25 vs 33
 
Instantiated on a CV syllable pronounced “chee”
	
192 disyllabic English words:
 
 
96 with a weak-strong syllable accent
 
96 with a strong-weak syllable accent
 
	
4 English sentences:
 
2 well-formed prosodic sentences 2 prosodically ill-formed sentences
 
Two English passages

Familiarization Phase	30s Tone 25 or 33	4 music trials	
2 versions of the same sequence:
 
 
One prosodically well-formed (bold)
 
One prosodically ill-formed (italics)
 
 
John doesn't know what rabbits eat. Leafy vegetables taste so good. They don't cost much either.

Test Phase	
8 trials:
 
 
4 Alternating (i.e., 25 33 25 33 ... or 33 25 33 25 ...)
 
4 Non-Alternating (i.e., 25 25 25 25... or 33 33 33 33...)
 
	
16 trials :
 
 
8 weak-strong lists with 12 words each (e.g., comply, befall, depart...)
 
8 strong-weak lists with 12 words each (e.g., pliant, falter, comet...)
 
	
2 passages:
 
 
One including the well-formed sentence.
 
The other including the ill-formed sequence.
 

Fig. 3. Summary of proposed methods.

**Vocabulary:** The Oxford Communicative Development Inventory (O-CDI), a parental questionnaire, will track infants' word comprehension and production at each time point.

**Cognitive Development:** The Bayley Scales will assess broader cognitive development at 7.5, and 12 months.

**Experiment Duration:** Each experiment will last approximately 5 minutes, with each visit lasting around one hour to allow parents time to complete the O-CDI and provide infants with breaks between experiments to minimise fatigue.

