**SHORT TITLE/ACRONYM**

**Predictions:** Based on previous findings Preterm groups are expected to show delayed acquisition of these properties compared to the full-term group. If, as predicted, the delay stems from a lack of prenatal prosody exposure, the delay will appear in the Standard-Care-group but not in the Womb-Simulated-group.

**Analyses:** Data on looking times, vocabulary, and cognitive development will be collected and compared across the three study groups. Analyses will be conducted using linear mixed-effects models, which are particularly suitable for handling missing data in longitudinal studies with repeated measurements.

Analyses will be conducted using R and the lme4 package to fit linear mixed-effects models. Fixed effects will include Group (womb-simulated preterm, standard-care preterm, full-term), Age (7.5, 9, 10.5, 12 months), and Stimulus Type (e.g., alternating vs. non-alternating). Participants and stimuli will be included as random effects. Model selection will follow a stepwise comparison approach, retaining the model with the lowest BIC and a significant log-likelihood ratio test. A typical model will take the form:

`lmer(TotalLook~Group*Age*StimType+(Age|SubjectID)+(1|Stimulus)).`

P-values will be derived from F-values using the Satterthwaite approximation. Planned comparisons will use orthogonal contrasts. While SES, gestational age, and birth weight will not be included in the primary models, their effects will be explored in secondary analyses. All analyses will be pre-registered and conducted in line with open science practices.

Data will be summarised using descriptive statistics and visualised with graphs to illustrate group differences and developmental trajectories. Demographic matching of full-term infants will further strengthen causal inference by reducing potential confounding factors.

**Dissemination Activities:** Co-designed resources such as infographics, videos, animations, and a website will target families and practitioners. Workshops for families, practitioners, and

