**SHORT TITLE/ACRONYM**

Sample size calculations were informed by prior research on early speech perception and language development in preterm infants, which report medium to large effect sizes ( $d = 0.59\text{--}0.80$ ). Power calculations ( $\alpha = 0.05$ , power = 0.80) conducted using G\*Power (version 3.1) indicate that this sample size is adequate to detect meaningful group differences in language and cognitive outcomes. This sampling strategy directly addresses the study's aim of identifying whether early auditory experience influences language development trajectories.

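### No primary outcome or contrast is named: five or six efficacy measures share an unallocated 5%, giving up to a 12–14% chance of a false positive favouring the intervention if the tests are independent

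*Protocol*

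**What the plan says.** Protocol section 2.2 lists three efficacy domains: prosody, vocabulary and cognition. The vocabulary entry covers two scores: "Vocabulary comprehension and production – assessed through parental report questionnaires". Then comes "Secondary outcomes include", under which the only item is feasibility and acceptability. The closing sentence gives the whole list the same job: "These outcomes will allow us to evaluate whether exposure to a womb-like auditory environment can support early language and cognitive development in preterm infants".

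Section 3 (Measuring Language Outcomes) gives the protocol's own count: "WP3 includes three experiments on prosody development, one vocabulary measure, and one general cognitive development measure over five months". That is five measures. Later in section 3 the vocabulary questionnaire (O-CDI) "will track infants' word comprehension and production at each time point", so it can yield two outcomes rather than one.

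Alpha 0.05 and power 0.80 appear only in the sample-size text, in section 3 (Participants) and section 5.2.1. They go with a range of effect sizes, d = 0.59 to 0.80, and no outcome or comparison is attached. Section 5.2.1 then calls the sample "adequate to detect meaningful group differences in language and cognitive outcomes", covering both domains at once.

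The analysis text in section 3 compares looking times, vocabulary and cognition across the three groups. Its example model crosses group, age and stimulus type. "P-values will be derived from F-values using the Satterthwaite approximation", and planned comparisons are to be orthogonal contrasts that are not listed. The text does not say which term or contrast answers the womb-simulated versus standard-care question.

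**The concern.** A reader of section 2.2 cannot tell which result would count as showing that the intervention works. As written, a significant difference on any one of the three prosody experiments, on vocabulary or on cognition could be reported as support. Each would be tested at 5%, with no statement of how the 5% is shared.

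Two things follow. The risk of a spurious positive finding across the set exceeds the risk for any single test. And the stated power describes no particular test, so nobody can check whether the sample is large enough for the question that matters most.

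A method of adjustment can reasonably sit in an analysis plan. The ranking of outcomes, and the test that the sample size serves, belong in the protocol. Sections 2.2 and 5.2.1 attempt both and leave them unresolved.

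**Working it through.** **1. The protocol's own figure.** Three groups of 40 make 120. Inflating for 20% attrition gives 120 / (1 − 0.20) = 150, which matches the stated total.

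**2. Which test does the power refer to?** At alpha 0.05, power 0.80 and d = 0.59, the number per group depends on the test assumed:

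- two-sided two-group t-test: 46.1, so 47
- one-sided two-group t-test: 36.2, so 37
- three-group analysis of variance with f assumed to be d/2 = 0.295: 113.8 in total, so 38 per group

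At d = 0.80 the two-sided t-test needs 25.5, so 26. Forty per group fits several of these readings, and the document does not say which one was used.

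**3. Inputs for the error rate.**

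- Number of measures k: 5 (section 3, Measuring Language Outcomes), or 6 if O-CDI comprehension and production are separate.
- Level per test: 0.05. Sidedness is not stated. F-based p-values are non-directional, so I assume two-sided 0.05, which is 0.025 in each direction.
- Assumption: one womb-simulated versus standard-care test per measure.

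**4. Independent tests, no true effect.**

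- Any false positive, either direction, 1 − 0.95^k: k = 5 gives 1 − 0.7738 = 22.6%; k = 6 gives 1 − 0.7351 = 26.5%.
- At least one false positive favouring the intervention, 1 − 0.975^k: k = 5 gives 1 − 0.8811 = 11.9%; k = 6 gives 1 − 0.8591 = 14.1%.

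**5. Correlated tests.** The document gives no correlations, so these are assumed values. The figures come from one million simulated draws of equally correlated normal statistics.

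| Correlation | Either direction, k = 5 | Either direction, k = 6 | Favourable, k = 5 | Favourable, k = 6 |
|---|---|---|---|---|
| 0.3 | 20.9% | 24.2% | 10.5% | 12.2% |
| 0.5 | 18.3% | 20.7% | 9.1% | 10.4% |
| 0.8 | 12.7% | 13.9% | 6.4% | 6.9% |

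**6. If the favourable direction is not fixed for every measure.** Section 3 states a preferred pattern for Lexical Stress only. Suppose a difference either way on Lexical Tone and Prosodic Boundaries could be read as benefit, and the other measures count one way. Under independence the risk is then 1 − 0.95² × 0.975⁴ = 18% for six measures and 1 − 0.95² × 0.975³ = 16% for five.

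**7. Cost of the alternative remedy.** Splitting alpha equally (Bonferroni) at 40 per group, two-sided, by normal approximation:

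| Measures | Alpha each | Power at d = 0.59 | Power at d = 0.80 | Per group for 80% power at d = 0.59 |
|---|---|---|---|---|
| 5 | 0.05/5 = 0.010 | 53% | 84% | 68 |
| 6 | 0.05/6 = 0.0083 | 50% | 83% | 70 |

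Without a split, power at d = 0.59 is 75% on the same approximation (74% by t-test).

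**The case against.** The best defence is that the protocol does give direction. The predictions in section 3 concern prosody: a delay is expected under standard care and not in the womb-simulated group. Age enters one mixed model rather than four separate tests. All analyses are to be pre-registered, and adjustment across outcomes may sit in an analysis plan that is not shown.

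Much of this stands. The method of adjustment is not a finding here, and the four ages should not be counted as four tests. But the prediction covers three experiments and does not select one, and the promise to pre-register names no primary outcome.

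Several stronger readings are tempting and are not supported:

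- **A one-in-four chance of a false claim of benefit.** The 26.5% counts significant results in both directions over six independent tests. A result favouring standard care is not a claim of benefit, and section 3 predicts one direction. Even the looser reading in step 6 of the working gives 16–18%.
- **A figure of about 60%.** Six outcomes times three group contrasts gives 1 − 0.95^18 = 60%. Three groups allow at most two orthogonal contrasts, which is what the plan uses, and standard care versus full-term does not test the intervention.
- **That power was calculated for a single comparison, or that 0.05 is offered as a trial-wide error rate.** The protocol states neither.

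In the other direction, interaction terms and stepwise model selection could open more routes to a positive finding. The protocol does not fix how many would support a claim, so no figure follows.

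**Conclusion.** The point holds in this form. Section 2.2 puts five or six efficacy measures on an equal footing with no primary outcome or contrast, and the stated alpha and power belong to no identified test. The chance of at least one false positive favouring the intervention is 11.9% for five measures and 14.1% for six. In either direction it is 22.6% and 26.5%. Even the lowest independent figure, 11.9%, is more than four times the 2.5% that one two-sided 5% test carries in the favourable direction.

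These figures assume independent tests, two-sided 0.05 for each, one womb-simulated versus standard-care test per measure, and a favourable direction fixed in advance. Positive correlation lowers the favourable figure, to about 9–12% at an assumed 0.3–0.5. An unfixed direction or more tests per measure would raise it. The fault should be corrected before outcome data are collected, but it does not invalidate the design.

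**What to change.** In section 2.2, name one primary outcome and one primary contrast, womb-simulated versus standard-care preterm infants, and state the model term and the age or ages that test it. A prosody measure fits the stated hypothesis. Lexical Stress is one option, because section 3 gives its expected direction; the ages at which it is run should be checked against Fig. 2, which is not available here. List the other two experiments, the O-CDI scores and the Bayley assessment as secondary.

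Restate the sample-size and power text in section 3 (Participants) and section 5.2.1 so that it refers to the primary test only, with the effect size assumed for it. How the secondary outcomes are adjusted, if at all, can be left to the analysis plan.

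The cost is wording, plus less confirmatory weight for the other outcomes. Keeping all the measures co-equal with a Bonferroni split costs more: power at d = 0.59 falls to about 50–53% with 40 per group, and 68–70 per group would be needed to restore 80%.
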